Study drug administration will continue from the time of enrollment until the time of repeat biopsy (12 month), disease progression or until off study (see *CRITERIA FOR EVALUATION AND ENDPOINT DEFINITION*). The planned/maximum duration of

treatment is one year. A total of 72 bottles of study drug (4,320 capsules) will be distributed per subject over the 12-month treatment period.

Contraindications

Noni is contraindicated in subjects who are hypersensitive to Noni products or any of the inactive ingredients found in the drug product capsules.

Concomitant Medications

During study participation, subjects may not consume any additional Noni extract. Subjects consuming the equivalent of an additional 1,000 mg of Noni extract will be considered noncompliant, and will have the study requirements re-explained to them up to two separate visits. Persistent non-compliance for 6 months may result in removing the subject from study.

Participants may not take anticoagulants, such as heparin, or Coumadin or steroid hormones or medications, which have known impact on PSA. If a subject begins taking these medications after being enrolled, they will be withdrawn, taken off study drug and replaced.

A list of supplements and medications to avoid is provided in **Appendix B**.

All medications (prescription and over-the-counter), vitamin and mineral supplements, nutritional supplements and/or tea consumption by the participant following signing of the informed consent will be documented on the concomitant medication CRF and will include: start and stop date, dose and route of administration, and indication. Medications taken for a procedure (*e.g.*, biopsy) will also be documented.

Dose Modifications

Subjects will be assessed clinically for adverse events during screening, prior to enrollment, at one month during intervention, quarterly during intervention, and at the end of intervention. Blood will be drawn at each of these study visits to assess for any adverse events. Any adverse events occurring during the investigation will be managed according to standard medical practice.

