AEs requiring dose suspension or permanent discontinuation of Noni extract are listed in the table below. Following any LFT elevation or INR increase, study drug will be withheld (grade 1) or permanently discontinued (grade ≥2), and liver function and PT/PTT monitored weekly until resolution to normal. Study drug may be resumed when laboratory values return to within reference range and will continue to be monitored weekly for 4 consecutive weeks. Study drug will also be permanently discontinued for grade 3 and 4 AEs, unless clearly not related to therapy. For grade 3-4 AEs not related to Noni extract,

we will suspend the study drug, and notify the site investigator and study PI. Noni extract may be reintroduced if AE resolves within 3 weeks.

Adverse events affecting LFT and/or PT/PTT levels will be monitored weekly until AE resolves. There are no reductions in the Noni extract dose; if AEs occur that require suspension of drug administration, the dose will remain the same once treatment resumes. Subjects who have had an interruption of intake of more than 30 calendar days may be withdrawn from the study at the discretion of the investigator. Subjects who have an unresolved AE at the time of withdrawal from study treatment will continue to be followed until resolution of the event, if possible. If an AE persists for more than 30 days after a subject goes off study, the subject will be referred to his personal physician.

Rules for Dose Suspension and Discontinuation

Event ¹	Action
Grade 1 LFT ² elevation	Suspend study drug; notify site investigator and study PI. Perform at least weekly LFTs until recovery to normal; study drug may be reintroduced if recovery occurs ≤ 2 weeks after drug discontinuation, with approval of the study PI and site investigator. After reintroducing drug, perform at least weekly LFTs. Any elevation of LFTs after drug discontinuation will results in permanent discontinuation of drug.
Grade ≥2 LFT elevation	Permanently discontinue study drug; notify site investigator and study PI. Monitor at least weekly until recovery to normal.

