Grade 1 Prothrombin Time prolongation or INR increase	Suspend study drug; notify site investigator and study PI. Perform at least weekly PT/PTTs until recovery to normal; study drug may be reintroduced if recovery occurs \leq 2 weeks after drug discontinuation, with approval of the study PI and site investigator. After reintroducing drug, perform at least weekly PT/PTTs. Any prolongation of PT/PTTs after drug discontinuation will results in permanent discontinuation of drug.
Grade ≥2 PT prolongation or Grade ≥2 INR increase	Permanently discontinue study drug; notify site investigator and study PI. Monitor at least weekly until recovery to normal.
Bleeding of the mouth and gums, easy bleeding or bruising, frequent nosebleeds	Suspend study agent until event resolves. If study drug is reintroduced and AE returns, permanently discontinue study drug.
Grade 1 AE not related to liver function AND lasting less than four weeks, regardless of drug attribution	No suspension required; capture AE information according to standard procedures.
Grade 2 AE not related to liver function AND not related to therapy	No suspension required; capture AE information according to standard procedures.
Grade 1 AE that persist for greater than 4 weeks AND related to therapy	Suspend study agent until event resolves. If study drug is reintroduced and AE returns, permanently discontinue study drug.
Grade 2 AE AND related to therapy	Suspend study drug; notify site investigator and study PI. Study drug may be reintroduces if AE resolves within 2 weeks. If study drug is reintroduced and AE returns, permanently discontinue study drug.
Grade 3 or 4 AE AND not related to therapy	Suspend study drug; notify site investigator and study PI. Noni extract may be reintroduced if AE resolves within 3 weeks and with approval of the site investigator.
Grade 3 or 4 AE AND related to therapy	Permanently discontinue study drug; notify site investigator and study PI.
Development of clinical evidence of disease progression	Permanently discontinue study drug; notify site investigator and study PI.

¹AEs classified as unlikely, possibly, probably or definitely related to drug are to be considered related to therapy when assessing drug attribution for dose modification.

Page 16 of 38

Replacement

All participants that meet the following criteria will be replaced:

- Patients who discontinue treatment before completing 12 months of the study treatment for reasons other than progression of disease.

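### For some grade 2 or worse liver-test and PT/INR events, the dose rules order a permanent stop in one place and allow a restart in another, and do not say which prevails

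*Combined protocol and SAP*

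**What the plan says.** The rules are in TREATMENT PLAN, in the Dose Modifications text and the table headed Rules for Dose Suspension and Discontinuation.

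**Rules ordering a permanent stop.** The text reads: "Following any LFT elevation or INR increase, study drug will be withheld (grade 1) or permanently discontinued (grade ≥2". No attribution condition is attached. The table has a row for LFT elevation of grade 2 or more and a row labelled "Grade ≥2 PT prolongation or Grade ≥2 INR increase". Both order permanent discontinuation.

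**Rules allowing a restart.**
- The general row for related grade 2 AEs suspends drug and adds: "Study drug may be reintroduces if AE resolves within 2 weeks".
- The general row for unrelated grade 3 or 4 AEs suspends drug and adds: "Noni extract may be reintroduced if AE resolves within 3 weeks and with approval of the site investigator". The text gives the same permission without the approval condition: "Noni extract may be reintroduced if AE resolves within 3 weeks".
- Directly after the permanent-stop rule the text says: "Study drug may be resumed when laboratory values return to within reference range". This sentence is not limited to grade 1.

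**Footnotes and exclusions.** Footnote 1 treats every attribution class except not related as related, including unlikely. Footnote 2 lists PT/PTT among the liver-function tests. The two rows that require no suspension exclude liver events; one is labelled "Grade 2 AE not related to liver function AND not related to therapy". The two restart rows have no such exclusion.

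**The concern.** LFT and PT/INR changes are the laboratory signals this protocol singles out for stopping drug, so the rule for them should have one reading. An abnormal laboratory finding is an AE under the protocol's own definition (REPORTING ADVERSE EVENTS), so the general rows do reach these events.

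Drug is dispensed at more than one site and the dose is not reduced on restart. A site applying a general row could put a man back on 6,000 mg/day when another site would stop him permanently. The choice also affects enrolment: under Replacement, a man who stops before 12 months for a reason other than progression is replaced.

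The general rows also carry weaker safeguards than the grade 1 rows. Restart after a grade 1 LFT or PT/INR event needs approval from both the study PI and the site investigator, then at least weekly tests. The related grade 2 row states no approval for restart, the unrelated grade 3 or 4 row needs only the site investigator's approval, and neither asks for weekly tests afterwards.

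**Working it through.** There is no planned figure to reproduce. The check matches each type of event to every rule whose wording it meets, then sizes the difference in exposure.

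**Step 1. Match events to rules (LFT or PT/INR events, grade 2 or more).**

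| Event | Named rows and text | General row that also fits | Result |
|---|---|---|---|
| Grade 2, related | Permanent stop | Suspend; restart allowed if resolved within 2 weeks | Conflict |
| Grade 2, not related | Permanent stop | None: the row excludes liver function, and footnote 2 counts PT/PTT as liver function | No conflict in the table |
| Grade 3-4, related | Permanent stop | Permanent stop | Agree |
| Grade 3-4, not related | Permanent stop | Suspend; restart allowed if resolved within 3 weeks (table and text) | Conflict |

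That is 2 of 4 cells. No sentence in the protocol says that the named rows override the general ones or that the stricter action applies.

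**Step 2. Count by attribution class.** The protocol has five classes (not related, unlikely, possibly, probably, definitely), and footnote 1 makes four of them related.
- Combinations: 3 grades x 5 classes = 15.
- Conflicts: grade 2, 4 of 5; grade 3, 1 of 5; grade 4, 1 of 5. Total 4 + 1 + 1 = 6 of 15.

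This counts combinations of labels. It is not a proportion of patients.

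**Step 3. Extra exposure per affected man.** Inputs:
- Supply (Dose Regimen and Dose Groups): "A total of 72 bottles of study drug (4,320 capsules) will be distributed per subject over the 12-month treatment period".
- Daily dose: 4 + 4 + 4 = 12 capsules.
- Treatment length: 4,320 / 12 = 360 days.
- On-treatment blood draws: PT/PTT at months 1, 3, 6 and 9; metabolic panel at months 3, 6 and 9.

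Assumptions: 30-day months; the event is found and drug stopped at a scheduled draw; restart on day 14 (related grade 2) or day 21 (unrelated grade 3-4); uninterrupted dosing to day 360.

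Added days compared with a permanent stop = 360 - 30 x month - 14 (or 21).

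| Found at | Grade 2, related | Grade 3-4, not related |
|---|---|---|
| Month 1 (PT/PTT only) | 360 - 30 - 14 = 316 | 360 - 30 - 21 = 309 |
| Month 3 | 360 - 90 - 14 = 256 | 360 - 90 - 21 = 249 |
| Month 6 | 360 - 180 - 14 = 166 | 360 - 180 - 21 = 159 |
| Month 9 | 360 - 270 - 14 = 76 | 360 - 270 - 21 = 69 |

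Restart before day 14 or 21 would add more days; a later interruption would remove some.

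**Step 4. Effect on the analysis.** Under Primary Endpoint, an eligible man with at least one dose and a post-treatment biopsy is evaluable. The end-of-intervention procedures, including biopsy, are to be done when possible after early discontinuation. The choice of row therefore does not by itself decide evaluability, and no sample-size or power figure depends on it.

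**The case against.** The strongest reply is that the specific rule governs the general one, and that both can be obeyed together. The named rows are mandatory and the general rows only permit a restart, so a site that stops permanently breaches neither. Several features support this as the intent:

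- After the LFT/INR rule, the text says drug will *also* be stopped for grade 3 and 4 AEs, which reads as a further category of events.
- A permanently discontinued drug cannot be resumed, so the resumption sentence, with its weekly monitoring, most naturally belongs to grade 1.
- If the general rows governed, a related grade 2 LFT event could restart while an unrelated one could not.
- The liver exclusion is most needed in the rows that keep drug going; the two restart rows already suspend it.
- Both restart rows require that the site investigator and the study PI be notified, so one person hears of every case.
- The phase I study described under Clinical Experience (51 patients, maximum tolerated dose 12 g) reported no dose-limiting adverse events.

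Most of this stands as evidence of intent, and PI notification does limit divergence between sites. It does not remove the written permission to restart. The reader has to infer precedence, while the exclusion in two neighbouring rows and its absence from these two invites the opposite inference. The phase I result makes events less likely to be common, but it gives no rate of LFT or PT/INR events for 12 months at this dose.

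**Conclusion.** The concern holds as a minor point of wording. Two stated safety rules conflict for LFT and PT/INR events that are grade 2 and related, or grade 3-4 and not related: 2 of 4 cells, 6 of 15 combinations. The other two cells do not conflict in the table. The likely intent is the permanent stop.

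For a man handled under the general rows, the difference is 69 to 316 further days at full dose, on the assumptions in the working. How many men this would affect cannot be estimated from the documents. The consequences are for safety conduct and replacement; no sample size, power or endpoint figure changes.

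**What to change.** Keep the permanent stop and make four wording changes:

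1. In the general rows for related grade 2 AEs and for unrelated grade 3 or 4 AEs, add: other than LFT or PT/INR events.
2. Add the same exclusion to the sentences on grade 3-4 AEs in the Dose Modifications text.
3. Limit the resumption sentence in that text to grade 1 events.
4. Add one sentence: the LFT and PT/INR rows take precedence over the general AE rows.

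The fourth change alone would settle the table; the others stop the text from reopening the question.

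The cost is an edit to one table and one section of text at the next amendment, with no extra visits, tests or patients. The downside is that a man with a clearly unrelated, resolved grade 3-4 LFT or PT/INR event cannot restart, which the named rows already imply.

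### The bleeding row of the dose table has no grade or attribution bound, so a related grade 3-4 event of the signs it lists meets two incompatible rules

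*Combined protocol and SAP*

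**What the plan says.** The table under Rules for Dose Suspension and Discontinuation lists events and actions. One row is defined by signs alone: "Bleeding of the mouth and gums, easy bleeding or bruising, frequent nosebleeds". Its action reads "Suspend study agent until event resolves. If study drug is reintroduced and AE returns, permanently discontinue study drug". The row states no grade, attribution, deadline for resolution, approval or notification.

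The other general rows are defined by grade, attribution and, for grade 1, duration:

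- "Grade 3 or 4 AE AND related to therapy": the action is "Permanently discontinue study drug; notify site investigator and study PI".
- "Grade 1 AE not related to liver function AND lasting less than four weeks, regardless of drug attribution" and "Grade 2 AE not related to liver function AND not related to therapy": the action for both is "No suspension required; capture AE information according to standard procedures".
- Grade 2 related, grade 3-4 unrelated, and related grade 1 events lasting more than 4 weeks each have a row of their own.

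The text above the table, under Dose Modifications, repeats the grade 3-4 rule: "Study drug will also be permanently discontinued for grade 3 and 4 AEs, unless clearly not related to therapy". Footnote 1 to the table counts every attribution except not related as related, including unlikely. Under Severity of AEs and Assessment of relationship of AE to treatment, every adverse event receives a grade and an attribution.

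**The concern.** An event with the listed signs is also an adverse event with a grade and an attribution, so in most cases it falls under a graded row as well. The two rows do not always prescribe the same thing, and the protocol does not rank them. The sharpest case is a related grade 3 or 4 event, where one rule foresees a possible restart and the other ends treatment.

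Bleeding is a hazard the protocol takes seriously. Anticoagulants are excluded, PT/PTT is measured at months 1, 3, 6, 9 and 12, and the background names coumadins among the constituents. Drug is dispensed at several investigational sites, so different readings of the table are a practical possibility. The reading chosen can determine whether a man discontinues. Under Replacement, discontinuing before 12 months for a reason other than progression is a criterion for replacing him.

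**Working it through.** No sample size, power or event count enters this point. The check sets the bleeding row against the graded row for each kind of event it could cover.

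**Inputs.** The event and action columns of the table, its footnote 1, and the grade 3-4 sentence under Dose Modifications.

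**Cells.** Grade 1 is split at 4 weeks. Its shorter part is one cell, because that row applies whatever the attribution. Grade 1 over 4 weeks, grade 2, and grade 3-4 are each split into related and not related. That gives 1 + 2 + 2 + 2 = 7 cells. The bleeding row's action is the same in all of them: suspend until resolution, and stop permanently if the event returns after a restart.

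| Event with the listed signs | Graded row | Compared with the bleeding row |
|---|---|---|
| Grade 1, under 4 weeks, any attribution | Suspension not required | Bleeding row stricter |
| Grade 1, over 4 weeks, related | Suspend until resolution; permanent stop on return | Same action |
| Grade 1, over 4 weeks, not related | None | No overlap |
| Grade 2, related | Suspend and notify; restart only if resolved inside 2 weeks; permanent stop on return | Graded row stricter (time limit, notification) |
| Grade 2, not related | Suspension not required | Bleeding row stricter |
| Grade 3-4, related | Permanent stop and notify | **Incompatible** |
| Grade 3-4, not related | Suspend and notify; restart only if resolved inside 3 weeks and with approval | Bleeding row adds a permanent stop on return; graded row adds the time limit, approval and notification |

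**Count.** 1 incompatible + 4 differing in strictness + 1 identical + 1 without a graded row = 7.

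**Why only one cell is incompatible.** Where a row says that suspension is not required, it does not forbid suspension, so a site that suspends breaks neither row. In the grade 2 related and grade 3-4 unrelated cells both rows suspend, and the extra conditions can be applied on top of one another. In the grade 3-4 related cell this does not work: if the first event ends treatment, the bleeding row's provision for a restart and for recurrence has nothing left to apply to.

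**Is there a backstop elsewhere?** Dose Modifications lets the investigator withdraw a man whose intake has been interrupted for more than 30 days. This is discretionary and general. It neither ranks the rows nor replaces the 2-week and 3-week conditions.

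**The case against.** The strongest reply is a harmonising one: the bleeding row, being specific, displaces the general rows at grades 1 and 2, while the Dose Modifications text still controls at grades 3 and 4. The wording lends this some support. The bleeding row's action matches that of the row for related grade 1 events lasting over 4 weeks, which suggests it was written for low-grade signs. That reading would remove the incompatibility, but the protocol does not state it. A site that simply let the specific row prevail would reach the opposite result for the same man.

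A second reply is that footnote 2 lists PT/PTT among the liver function tests, so a bleed with abnormal PT/PTT may fall outside the two rows limited to events not related to liver function. Such a bleed would also meet the separate PT/INR rows. This could narrow the grade 1 and grade 2 unrelated differences. It leaves bleeding with normal PT/PTT where it was and does not touch the grade 3-4 related row, which has no such limit.

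Several stronger claims that a reader might infer are not supported:

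- *That the row covers all bleeding.* It names particular signs; other bleeding meets only a graded row.
- *That it authorises a restart.* Other rows say the drug may be reintroduced. This one only says what happens if it is. Restart is implied, not granted.
- *That the actions are opposite in three cells.* In two of those, grade 1 under 4 weeks and grade 2 unrelated, the rows differ only in strictness.
- *That the choice of row settles whether a man counts among the 30, or how tolerability reads.* Under Primary Endpoint, an eligible man is evaluable after one dose and a post-treatment biopsy, so a replaced man may still be evaluable. Adverse events are recorded with grade, attribution and action taken whichever row is followed.

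The documents give no expected frequency for grade 3-4 events of these signs, and the background reports no dose-limiting adverse events in the 51-patient phase I study. The case may be rare. That limits the urgency but does not resolve the conflict.

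**Conclusion.** The point stands as an internal inconsistency in the safety rules. For a related grade 3-4 event of the listed signs, the bleeding row on one side and the graded row with the Dose Modifications text on the other cannot both be followed. In four of the other six cells the rows differ in strictness without being incompatible. Because footnote 1 counts even an unlikely attribution as related, the incompatible cell takes in every grade 3-4 event of these signs except those judged not related.

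This rests on two assumptions: that the listed signs can reach grade 3 or 4, which the row does not exclude, and that no precedence rule exists outside the documents reviewed. The established consequence is that sites could handle the same event differently, including whether the man discontinues and meets a replacement criterion. No effect on the primary analysis is shown. The change should be made because two stated safety rules disagree for the same patient, not because many events are expected.

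**What to change.** Reconcile the bleeding row with the grade 1, grade 2 and grade 3-4 rows and with the Dose Modifications text. Either of two edits would do:

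1. give the bleeding row explicit grade and attribution bounds, so that each event falls under one rule; or
2. add one sentence to the table saying which row governs when an event meets two.

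Whichever is chosen, state whether the time limits, approval and notification steps of the graded rows also apply to the listed signs, and make the Dose Modifications text agree with the table. The investigators and the DSMC decide which action applies to which event; this review takes no view on that.

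The cost is one table row or one sentence, plus a matching edit to the text, in an amendment. No new procedures or data are needed.

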- Patients that are enrolled but do not receive any study treatment.
- Patients who were unable or unwilling to be in compliance with study requirements or were discontinued from study treatment in the judgment of the Principal Investigator.
- Patients for whom paired biopsies are not available for evaluation and endpoint assessments.

Adherence/Compliance

During study participation, subjects will be asked to: self-administer the study medication; avoid consumption of additional Noni and complete daily drug logs to record study agent intake. Subjects are expected to: maintain ≥85% compliance with study agent intake; comply with dietary, medication and supplement restrictions; and complete drug logs to the best of their ability. Subjects will be interviewed at the quarterly clinic visits, and pill counts will be performed to verify compliance with study requirements. Subjects discovered not to be complying with study requirements will have the requirements reexplained to them up to two separate visits. Persistent non-compliance for 6 months could result in removing the subject from study.

Plasma scopoletin, by will be measured with HPLC-EC at baseline, months 6, 9, and at the end of intervention as an objective marker of compliance and to correlate changes in plasma scopoletin levels to changes in clinical, biochemical and molecular targets.

PHARMACEUTICAL INFORMATION

Noni

Noni study drug is supplied through an agreement with Healing Noni (Hilo, HI). The Noni plant is a small evergreen tree that grows along Hawaii's beaches and in forest areas up to 1,300 feet. The plant has a straight trunk, large, bright green and elliptical leaves, white tubular flowers and distinct, ovid, "grenade-like" yellow fruit. The fruit can grow to 12 cm or more and has a lumpy surface covered by polygonal-shaped sections. Its seeds are triangular shaped and reddish brown. To manufacture Noni extract, a proprietary technique to dehydrate and concentrate the Noni fruit into powder was developed. Once dried, the final product contains of over 140 chemical components, including flavonoids, coumadins, anthraquinones, and iridoid glycosides. It has been used for centuries by the Hawaiians to treat heart problems, diabetes, high blood pressure, arthritis, and other degenerative ailments.

²Tests used to monitor liver function include: albumin, total and direct bilirubin, alkaline phosphatase, AST, ALT, total protein and PT/PTT

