All AEs that are reported by the subject, detected during a visit, physical examination, or laboratory work-up must be recorded in the participant's medical record and recorded on the CRF. All AEs that occur after the informed consent is signed must be recorded on the AE CRF whether or not related to study agent.

Data Elements

- AE reported date
- AE Verbatim Term

Page 31 of 38

- CTCAE Term (v 4.0)
- Event onset date and event ended date
- Severity grade
- Attribution to study agent (relatedness)
- Whether or not the event was reported as a Serious AE (SAE)
- Action taken with the study agent
- Whether or not the subject dropped due to the event
- Outcome of the event
- Comments

Severity of AEs

Identify the AE using the NCI Common Terminology Criteria for AEs (CTCAE) version 4.0. The CTCAE provides descriptive terminology and a grading scale for each AE listed. A copy of the CTCAE can be found at http://ctep.cancer.gov.

AEs will be assessed according to the CTCAE grade associated with the AE term. AEs that do not have a corresponding CTCAE term will be assessed according to their impact on the participant's ability to perform daily activities as follows:

Grade	Severity	Description
1	Mild	Barely noticeable, does not influence functioning
		Causing no limitations of usual activities
2	Moderate	Makes participant uncomfortable, influences
		functioning
		Causing some limitations of usual activities
3	Severe	Severe discomfort, treatment needed
		Severe and undesirable, causing inability to carry
		out usual activities
4	Life	Immediate risk of death
	threatening	Life threatening or disabling
5	Fatal	Causes death of the participant

Assessment of relationship of AE to treatment

Relationship of the AE to study drug will be classified as one of the following: not related, unlikely, possibly, probably, definitely. All AEs will be considered due to drug (AEs classified as unlikely, possibly, probably or definitely) unless clearly not related to therapy. The severity and seriousness of each AE will be assessed by the site investigator.

Follow-up of AEs

All AEs, including lab abnormalities that in the opinion of the investigator are clinically significant, will be followed until resolution, if possible. If an AE persists more than 30 days after the subject goes off study, the subject will be referred to his personal physician.

SERIOUS ADVERSE EVENTS (SAEs)

Definition: As those events, occurring at any dose, which meet any of the following criteria:

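### The footnote defining LFTs takes in PTT, albumin and total protein, so the dose-stopping table gives one PTT result two different actions and leaves some falls in albumin with no row

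*Combined protocol and SAP*

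**What the plan says.** Footnote 2 of the table Rules for Dose Suspension and Discontinuation is keyed to the grade 1 LFT row. It lists the tests as "albumin, total and direct bilirubin, alkaline phosphatase, AST, ALT, total protein and PT/PTT". The two liver rows fire on grade 1 elevation (suspend, possible restart) and on "Grade ≥2 LFT elevation" (permanent stop). The re-stop clause of the grade 1 row has the same direction: "Any elevation of LFTs after drug discontinuation will results in permanent discontinuation of drug". The text under Dose Modifications agrees: "Following any LFT elevation or INR increase, study drug will be withheld (grade 1) or permanently discontinued (grade ≥2".

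Coagulation has its own rows. The grade 1 trigger is "Grade 1 Prothrombin Time prolongation or INR increase", and the grade 2 or higher trigger is again PT or INR. Neither names PTT, but the grade 1 row's re-stop clause reads "Any prolongation of PT/PTTs after drug discontinuation will results in permanent discontinuation of drug". Dose Modifications mentions LFT and PT/PTT as two separate groups. The blood collection table draws PT/PTT in its own citrate tube and places the hepatic panel within the CMP.

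The general rows follow. Two of them require no suspension and exclude liver events: short grade 1 events, and "Grade 2 AE not related to liver function AND not related to therapy". The other general rows carry no liver exclusion. They cover related grade 1 beyond four weeks, related grade 2, unrelated grade 3-4 and related grade 3-4. Footnote 1 counts even an unlikely relationship as related.

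**The concern.** A stopping table should send each laboratory result to one action. Here one list serves as the definition of an LFT, one word (elevation) serves as the trigger for every test on it, and the PT/INR rows cover only part of the coagulation pair.

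Three things can follow. Two sites could take different actions on the same PTT result and both be within the protocol. A low albumin may have no liver row. A high albumin or total protein may suspend drug because of where the test is listed. The protocol singles out liver and coagulation: it excludes men with abnormal PT/PTT or on blood thinners, and checks PT/PTT at every on-treatment visit. Under Replacement, men who discontinue before 12 months for reasons other than progression are replaced, so inconsistent permanent stops could also affect who supplies the paired biopsies.

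**Working it through.** The plan gives no figure to reproduce on this point. The check is to read each abnormality against every row of the table and see which rows fire.

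**1. Isolated PTT prolongation** (PT and INR normal, a prolonged PTT taken as an elevation)

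| Event | As an LFT (footnote 2) | General row that also fires | Same action? |
|---|---|---|---|
| Grade 1, under 4 weeks | Suspend, may restart | None (liver excluded) | Only one row |
| Grade 1, over 4 weeks, related | Suspend, restart if recovered within 2 weeks | Suspend until resolved | Restart conditions differ |
| Grade 2, related | Permanent stop | Suspend, may restart if resolved within 2 weeks | No |
| Grade 2, unrelated | Permanent stop | None (liver excluded) | Only one row |
| Grade 3-4, unrelated | Permanent stop | Suspend, may restart if resolved within 3 weeks | No |
| Grade 3-4, related | Permanent stop | Permanent stop | Yes |

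If PTT is instead read as separate from LFTs, as the Dose Modifications wording and the PT/INR rows suggest, other actions change too. Grade 1 under four weeks and unrelated grade 2 then need no suspension, against suspension and permanent stop in the middle column.

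PT itself raises no conflict between the LFT and PT/INR rows, which give the same action. The overlap with the general rows is wider than PTT: it applies equally to PT, AST, ALT and bilirubin, because the related grade 2 and unrelated grade 3-4 rows do not exclude liver events.

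**2. Fall in albumin**

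A fall is not an elevation, so no liver row fires at any grade. General rows catch a related grade 1 fall beyond four weeks, a related grade 2 fall and any grade 3-4 fall. If a fall counts as liver-related, the two no-suspension rows are closed to it and three cases have no row:

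- grade 1 under four weeks;
- grade 1 beyond four weeks, unrelated;
- grade 2, unrelated.

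The second case is a gap for any adverse event, not only albumin. The first and third arise from the liver exclusion.

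**3. Rise in albumin or total protein**

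Read literally, this is an LFT elevation and suspends drug at grade 1 whatever the attribution. Two steps are needed. The value must become an adverse event, which the section on collecting AE information supports for abnormal scheduled bloods. It must also be graded. Under Severity of AEs, "AEs that do not have a corresponding CTCAE term will be assessed according to their impact", and a symptomless value would then be grade 1. That no CTCAE term exists for such a rise is an assumption.

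To size this, assume: a 2.5% chance per draw of exceeding the upper limit with no drug effect; screening in range; normal values; draws at months 3, 6 and 9; the two tests independent; within-man correlation from 0 to 0.8.

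- Correlation 0, one test: 1 − 0.975³ = 7.3%. Two tests: 1 − 0.975⁶ = 14.1%, and 30 × 0.141 = 4.2 men.
- Correlation 0.5, 0.7 and 0.8 (numerical integration, conditional on screening in range), one test: 5.6%, 4.2% and 3.4%. Two tests, 1 − (1 − p)²: 10.8%, 8.3% and 6.6%. At 0.8, 30 × 0.066 = 2.0 men.

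Albumin is part of total protein. An assumed between-test correlation of 0.5 lowers the range only to about 6% to 13%.

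**The case against.** The strongest reply is that this is drafting and that a sensible investigator would apply the specific row over the general one. The Dose Modifications text supports permanent discontinuation for LFT elevations of grade 2 or higher. That reading would remove the clash between the LFT and general rows. It stands as a plausible reading, but the protocol states no such precedence, and it does not settle whether PTT is an LFT at all.

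Several stronger conclusions are tempting, and the documents do not support them.

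- A reader might infer that the liver and PT rows are the only per-patient safeguard for these risks. They are not: the table also has a bleeding and bruising row and the general rows, and the off-drug criteria allow stopping at the investigator's discretion.
- A reader might infer that falls in albumin go unnoticed. Most are caught by general rows. Since even unlikely counts as related, the grade 2 gap is limited to events judged not related. Adverse events affecting LFT levels are monitored weekly in any case.
- A reader might count the silence of the PT/INR row as a third conflicting action. A row that does not fire gives no instruction.
- A reader might blame footnote 2 for the whole PTT conflict. Part of it comes from general rows without a liver exclusion, so removing PTT from the footnote would leave the overlap for AST, ALT and bilirubin.
- A reader might take the 7% to 14% as men lost and replaced. It counts suspensions, after which drug may restart; no discontinuation rate has been calculated. On the same assumptions the five other CMP liver tests (two bilirubins, alkaline phosphatase, AST, ALT) would give 1 − 0.975¹⁵ = 31.6% at correlation 0 and 1 − (1 − 0.034)⁵ = 15.9% at 0.8. Most chance suspensions would therefore come from acting on any grade 1 value.
- A reader might infer that the liver and coagulation stop rate could not be interpreted. The AE form already records the CTCAE term, grade, attribution and action taken, so stops can be tabulated by test.

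Finally, that a rise in albumin or total protein is not liver injury is clinical knowledge from outside the documents.

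**Conclusion.** The point holds as an internal contradiction in a stated safety rule. It is clearest for isolated PTT prolongation, where related grade 2 and unrelated grade 3-4 events each meet two rows with different actions and no precedence. For a fall in albumin the gap is partial: three low-grade combinations, and only if the fall is classed as liver-related. For a rise in albumin or total protein, the literal trigger rests on the value being recorded as an adverse event and graded 1. The chance suspension rate of about 7% to 14% (2 to 4 of 30 men) is illustrative and depends on the assumed 2.5% limit and correlations.

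The PTT and albumin-fall findings rest on wording alone and need no simulation. Eligible treated men with a post-treatment biopsy remain evaluable for the primary endpoint. The plan should be corrected because the same result can lawfully be handled in two ways.

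**What to change.** Amend the table so that footnote 2, the LFT rows, the PT/INR rows, the general rows and the Dose Modifications text agree:

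- for each test in footnote 2, state which direction of abnormality counts;
- assign each test one governing row, with PTT, albumin and total protein named explicitly;
- state which row prevails when a specific and a general row both apply;
- align the liver exclusions in the no-suspension rows with the revised list, so that no graded event is left without a row.

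Which clinical action belongs to each test is for the sponsor and investigators to decide. In the report, tabulate suspensions and permanent stops by triggering test, using AE data already planned.

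The cost is one protocol amendment to one table and its accompanying text. All the tests are already drawn; no extra visits or patients are needed.
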